## Scientific Background

Connecting depressed and suicidal adolescents with mental health (MH) treatment can play a critical role in reversing the alarming trend of suicide. Currently, rates of linkage with treatment among depressed and suicidal youth identified in primary care are as low as 18%, and, in one survey, increase only to 32% with integrated MH services. Aside from structural barriers such as treatment availability and cost, the major barriers to MH care among at-risk adolescents are motivational. In order to be motivated to engage in care, an individual must first perceive themselves to be susceptible to depression and suicide, and understand that treatment can help reduce these risks. Even then, there may still be significant stigma around depression labels and MH treatment that keep them from acting. Digital interventions using mobile communication such as text messaging (TM) could be useful to address motivational barriers to MH care initiation in depressed/suicidal adolescents and their parents. Potential benefits include the ability to repeatedly prompt awareness of treatment targets in daily life and deliver on-demand tailored support. Recent studies suggest TM interventions may improve retention in MH care for depressed adolescents already in treatment. Yet, effective approaches to enhancing MH care initiation among adolescents remains unknown.

## Study Objectives

To increase rates of MH care initiation, we propose an automated TM intervention, “Text to Connect” (T2C), that aims to increase motivations in at-risk adolescents and their parents. We will develop and examine T2C using dissemination and implementation science principles, specifically, the RE-AIM framework, for balancing internal and external validity and optimizing uptake and sustainability. We will select the most salient of the following behavior change techniques: psychoeducation, cued mood monitoring, adolescent-parent communication prompts, cognitive bias modification, and cues to action. Intervention material will be tailored to baseline characteristics. We will begin with treatment development. In an initial usability phase, we will develop and iteratively refine the format and content of T2C based on feedback from stakeholders. Data will inform a subsequent feasibility trial comparing T2C with treatment as usual (TAU) using a stepped wedge design.

Aim 1 (Phase 1, Development). To develop T2C, a TM intervention to address motivational barriers to MH treatment initiation for depression and/or suicidal screen-positive adolescents and parents in pediatric primary care. We will collaborate with NuRelm and the Office of Academic Computing at WPIC and the Methods Core to develop T2C based on stakeholder feedback (adolescents, parents, pediatricians, MH clinicians).

Aim 1b (Phase 1b, Feasibility). To examine the feasibility of T2C in pediatric primary care clinics (n=2 clinics, 50 adolescents) using a stepped wedge design.

Hypothesis 1b: Readiness for MH care will be greater among adolescents in T2C vs adolescents referred during TAU. We will first conduct t tests for continuous variables and chi square tests for categorical variables to examine for baseline differences in demographic

and clinical variables. We will use generalized linear mixed models (nesting for site) to examine for between-intervention differences in readiness. Baseline characteristics that distinguish the groups will be included as covariates in models examining treatment effects.

Aim 2: Explore differential rates of service utilization (behavioral and physical health services) among youth who receive Text2Connect (T2C) versus Treatment As Usual (TAU).

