A stepped wedge design was selected for both ethical considerations and feasibility. First, the T2C intervention is unlikely to cause harm, and PCP stakeholders have expressed the need and desire for these tools. Thus, we will offer these interventions to all practices to maximize stakeholder feedback and optimize opportunities for implementation. In the proposed stepped wedge design, all practices start with Treatment As Usual-TAU-(i.e., PCP referral to Mental Health care) and are randomized to transition to implement T2C at different times. All clinics will be initially monitored for at least 2 months during TAU, followed by a staggered adoption of T2C. During each time period, a new clinic will begin to use T2C (order determined by block randomization. A web-based system will randomly assign the next clinic to begin.

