## **Statistical Considerations**

A stepped wedge design was selected for both ethical considerations and feasibility. A stepped wedge cluster randomized trial design involves the sequential random rollout of an intervention over multiple time periods following a “baseline” period when no cluster has been exposed. The

crossover is typically in one direction, from control to intervention, and continues until all of the clusters receive the intervention with observations taken from every cluster and at each time period. All 3 studies in the ETUDES Center, and specifically, T2C, will utilize this design. Prior to study start, each CCP study practice will be randomly assigned to switch from Treatment As Usual (TAU) to the intervention.

In the proposed stepped wedge design, all practices start with TAU (i.e., PCP referral to embedded MH care) and are randomized to transition to implement T2C at different times. All clinics will be initially monitored for at least 2 months during TAU, followed by a staggered adoption of T2C. During each time period, a new clinic will begin to use T2C (order determined by block randomization. A web-based system will randomly assign the next clinic to begin.

With regard to Hypothesis 1: We will conduct t tests for continuous variables and chi square tests for categorical variables to examine for baseline differences in demographic and clinical variables. We will use generalized linear mixed models (nesting for site) to examine for between-intervention differences in readiness. Baseline characteristics that distinguish the groups will be included as covariates in models examining treatment effects.

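### Hypothesis 1b tests superiority on readiness under a feasibility aim, but with two clinics the randomised order cannot support that test; restate it as estimation

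*Combined protocol and SAP*

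**What the plan says.** - Study Objectives gives Aim 1b as "To examine the feasibility of T2C in pediatric primary care clinics (n=2 clinics, 50 adolescents) using a stepped wedge design". The one hypothesis attached to it is "Readiness for MH care will be greater among adolescents in T2C vs adolescents referred during TAU". Aim 2, on service use, is exploratory.
- Statistical Considerations presents the framework as cluster randomised: "A stepped wedge cluster randomized trial design involves the sequential random rollout of an intervention over multiple time periods". What is randomised is the timing of the switch: "all practices start with TAU (i.e., PCP referral to embedded MH care) and are randomized to transition to implement T2C at different times". Study Design & Methods has the "order determined by block randomization".
- On the calendar, Statistical Considerations says only "All clinics will be initially monitored for at least 2 months during TAU, followed by a staggered adoption of T2C" and "During each time period, a new clinic will begin to use T2C". The number of periods is not stated.
- The analysis, given in Study Objectives and again in Statistical Considerations, is a generalized linear mixed model with nesting by site. Covariates are chosen from tests of baseline differences. No period term, alpha, sidedness, effect size or intracluster correlation is given.
- The RE-AIM paragraph of Statistical Considerations defines Reach, Adoption and Implementation as percentages, and the follow-up calls collect satisfaction and usability. None of these is named as settling Aim 1b, and none has a criterion.

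**The concern.** The aim asks whether T2C can be delivered in these practices. The hypothesis asks whether T2C works better than TAU on a motivational outcome. The randomisation is a single toss between two clinic orders, so it gives almost no basis for a comparative test.

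A p-value from the mixed model draws its apparent strength from the 50 adolescents, not from the allocation. It is valid only if readiness does not drift over calendar time and does not fluctuate by clinic and period, and two clinics can barely check either condition. Two misreadings are then possible. A small p could be taken as a randomised effect. A large p, which is likely even if T2C helps, could be taken as the answer to the feasibility aim.

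**Working it through.** **Inputs from the documents:** 2 clinics, 50 adolescents, all clinics starting in TAU, one clinic switching per period. The sample size has no stated derivation, so there is no figure of the plan's own to reproduce.

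**Assumptions:** two-sided alpha of 0.05; effects in SD units; the shortest layout, three periods, with clinic A at TAU/T2C/T2C and clinic B at TAU/TAU/T2C; equal cells, m = 50/6 = 8.33; no dropout.

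1. **Randomisation (needs none of the assumptions).** With k clinics, one per step, there are k! orders, and the smallest one-sided p is 1/k!. For k = 2 this is 1/2 = 0.50. For k = 3 it is 1/6 = 0.17, and for k = 4 it is 1/24 = 0.042, so four clinics is the fewest that could reach 0.05. With two clinics, exchanging the labels only reverses the sign of the clinic-and-period-adjusted estimate, so its two-sided p is always 1.

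2. **Precision with clinic and period in the model.** Let D1, D2, D3 be the clinic A minus clinic B difference in mean readiness in each period. The clinics differ in condition only in period 2, so the estimate is D2 − (D1 + D3)/2. Each D has variance 2/m, and the total is 2/m + (1/4)(4/m) = 3/m = 3/8.33 = 0.36. SE = 0.60 SD, and 1.96 × 0.60 = 1.18 SD. Approximate power is Φ(0.5/0.60 − 1.96) = 13% for a 0.5 SD effect and Φ(0.8/0.60 − 1.96) = 27% for 0.8 SD. Two four-period layouts give half-widths of 1.11 and 1.28 SD.

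3. **Information on clinic-by-period variation.** With T periods there are 2T cell means and T + 2 parameters (T periods, one clinic contrast, one treatment effect), which leaves T − 2 degrees of freedom. Three periods leave 1 df (t = 12.7), four leave 2 (t = 4.30) and six leave 4 (t = 2.78). The ±1.2 SD interval in step 2 assumes this variation is zero. It is a different interval from one judged on 1 df, which would be 12.7 × 0.60 = 7.6 SD either side.

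4. **Effect of ignoring that variation.** If each cell mean has extra variance v, the variance becomes 3(1/m + v) = 0.36 + 3v. The true size of a nominal 5% test is 2[1 − Φ(1.96 × √(0.36/(0.36 + 3v)))]. For assumed v of 1%, 2% and 5% of the total this is 6.0%, 7.0% and 10.0%. A period term does not remove this.

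5. **The model as written, with site but no period.** Within clinic A the T2C periods average 2.5 and the TAU period is 1. Within clinic B they are 3 and 1.5. Each gap is 1.5 periods, so the bias is 1.5 × the drift per period. Assumed drift of 0.1, 0.2 or 0.3 SD per period with no T2C effect gives bias of about 0.15, 0.30 or 0.45 SD. Simulation (20,000 runs, site as a fixed effect) gives false-positive rates of about 7%, 16% and 29%. The SE looks better: each clinic's contrast has variance 1/m + 1/(2m) = 0.18, and the average of two has 0.09, so SE = 0.30 SD. Half the SE of step 2 is gained by assuming that there is no time trend.

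**The case against.** - **A pilot may state a directional hypothesis, and this one is modest.** No alpha, decision rule or confirmatory claim is attached to it. Readiness is a proximal motivational outcome; under RE-AIM the plan defines efficacy as treatment initiation and engagement. This stands. A reader might infer that the plan commits to an efficacy decision, but the documents support only that superiority on readiness is the sole hypothesis under the aim.
- **The mixed model can still return p < 0.05.** It can, and such a result would not be shown to be false. It would depend on the model's assumptions and not on the randomisation.
- **The layout is assumed.** True. A reader might take the critical value of 12.7 as a property of this trial. It belongs to the shortest layout only, and more periods soften it. The two-order limit does not depend on the layout.
- **The excess error from clinic-by-period variance is mild.** At 1–2% of the variance it is. Time confounding in the model as written is the larger threat.
- **A 95% CI carries the same information as a 5% test.** Correct. The improvement comes from the period term, the stated conditioning and the absence of a significance claim, not from the interval itself.
- **Feasibility is already measured.** It is, through RE-AIM, satisfaction and usability. A reader might infer that the plan neglects feasibility; it does not. The lack of thresholds is mainly missing detail and does not carry this point.

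**Conclusion.** The point holds. With two clinics the randomised order cannot support Hypothesis 1b as a test: the limit of one-sided p = 0.50 follows from the stated clinic count alone. A significant result from the planned model would need independence within clinic and no secular trend, and the model names no period term.

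The sizes depend on assumptions. With three periods, equal cells and no dropout, the time-adjusted difference is known to no better than about ±1.2 SD, too wide to judge benefit. Clinic-by-period variance of 1–5% raises a nominal 5% test to about 6–10%. How the result would be reported cannot be known from the documents, so the consequence is a risk of misreading and not a demonstrated error.

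**What to change.** 1. **Reword Hypothesis 1b** as estimation of the T2C minus TAU difference in readiness, conditional on these two clinics, from a model with clinic and period as fixed effects. Report a 95% CI, state that it omits clinic-by-period variation, and make no significance or efficacy claim.
2. **State the limit** in Study Design & Methods and in Statistical Considerations: two clinics allow only two orders, so clinic-level randomised inference is not available.
3. **Base the Aim 1b conclusion on Reach, Adoption and Implementation**, as already defined in the RE-AIM paragraph, with exact CIs by clinic and overall, against criteria that the investigators set before the first switch. For scale, 20 of 25 T2C participants completing would give an exact 95% CI of 59–93%, and 40 of 50 would give 66–90%. The counts and split are illustrative, and the intervals ignore clustering. Reach and Adoption have their own denominators.

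The change needs no new clinics, participants or measures, only rewording of one hypothesis and the analysis text. The price is a wider interval once period is in the model and no confirmatory statement on readiness.

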## Study Design & Methods

T2C aims to increase perceived susceptibility/severity of depression/suicidality and decrease stigma in at-risk adolescents and their parents. We hypothesize that modification of patient beliefs leads to change talk, thereby increasing the experience of discrepancy which affects motivation for change. These experiences in turn influence decisional balance away from ambivalence toward readiness for change.

We propose the following behavior change techniques: psychoeducation, cued mood-monitoring, adolescent-parent communication prompts, cognitive bias modification, and cues to action. Psychoeducation will be used to increase understanding of: 1) how mood and behavioral symptoms signal depression/suicidality; and 2) the availability and benefits of MH services. Cued mood monitoring (i.e. daily mood reports) will raise awareness of personal severity of depression. Cognitive bias modification will shift beliefs around depression/suicidality, and stigma regarding MH treatment. Cues to action will strengthen the link between intentions and action. Prompts will include contact information and reminders to target barriers to scheduling and attending MH appointments.

Tailoring is the method of personalizing characteristics of an intervention (e.g., content, timing) to maximize receptivity and engagement. Tailoring within digital interventions has been shown to be an important to optimize effectiveness. In T2C, intervention material will be tailored to adolescents' and parents' baseline characteristics; based on characterization, we will prioritize specific T2C intervention material. For example, if an adolescent perceives themselves to have low readiness, the TM intervention will give greater weight to psychoeducation and cognitive bias modification.

A stepped wedge design was selected for both ethical considerations and feasibility. First, the T2C intervention is unlikely to cause harm, and PCP stakeholders have expressed the need and desire for these tools. Thus, we will offer these interventions to all practices to maximize stakeholder feedback and optimize opportunities for implementation. In the proposed stepped wedge design, all practices start with Treatment As Usual-TAU-(i.e., PCP referral to Mental Health care) and are randomized to transition to implement T2C at different times. All clinics will be initially monitored for at least 2 months during TAU, followed by a staggered adoption of T2C. During each time period, a new clinic will begin to use T2C (order determined by block randomization. A web-based system will randomly assign the next clinic to begin.

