#### Baseline assessment phone call:

Following the informed consent, the ARC assessor will conduct the baseline assessment measures. The measures include collecting sociodemographic questions, the CSSRS scale & suicide scales, quality of life ratings, treatment history, barriers to treatment, readiness for treatment, attitudes toward seeking psychological help, anxiety & mania adaptive scales via the K-CAT mental health adaptive screen, substance use, depression history, treatment preferences, and if there's a family history of bipolar disorder that impacts the youth's risk for mental health problems. A waiver of HIPAA authorization to collect permission verbally over the phone will be used to access and collect medical record data. Electronic medical record information will be used to supplement treatment and service utilization and uptake of the T2C intervention via the RE-AIM framework described in statistical analysis. Parents will respond to questions about their child, not themselves and youth will answer about themselves. Phone calls will take about 30-60 minutes.

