#### Follow Up assessment phone calls:

During each follow up assessment phone call during week 4 and week 12 following the baseline phone call and onboarding to T2C, the ARC assessor will update demographic & contact information, ascertain continuing consent and assent to participate in study, and collect measures on depression, anxiety, mania, and suicide symptoms, the CSSRS, quality of life ratings, barriers to treatment, readiness for treatment, depression literacy, treatment utilization and history since last assessment, substance use, and additionally information on client satisfaction and usability processes with the T2C intervention once the family has completed the program. The youth will respond to questions about themselves and the parent about their child. Phone calls will take about 30-60 minutes.

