In order to enhance uptake of T2C, we will conduct the proposed work within the RE-AIM framework, as follows. (R)each: The percentage and characteristics of screen-positive adolescents referred for MH treatment who are offered, and agree to participate in, T2C. (E)fficacy: The impact of T2C on MH treatment initiation and engagement. (A)doption: The percentage and characteristics of PCPs who refer to T2C upon making a referral for MH care for a screen-positive adolescent. (I)mplementation: The percentage and characteristics of patients who consent to T2C who complete the TM intervention. (M)aintenance: The percentage and characteristics of PCPs who recommend T2C to appropriate patients upon long-term follow-up, as well as T2C utilization by referred adolescents/parents via de-identified data. The baseline and follow up measures administered are mapped onto each component of the RE-AIM framework.

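### Follow-up suicide symptoms and the CSSRS have no planned post-baseline comparison of T2C with TAU, although the rollout rests partly on an untested assumption that T2C is low risk

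*Combined protocol and SAP*

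**What the plan says.** Study Design & Methods gives ethics and feasibility as the reasons for the stepped wedge. The ethical reason begins with the statement that "the T2C intervention is unlikely to cause harm, and PCP stakeholders have expressed the need and desire for these tools", and the offer to all practices follows from it. The same section describes the mechanism: "T2C aims to increase perceived susceptibility/severity of depression/suicidality and decrease stigma in at-risk adolescents and their parents", and "Cued mood monitoring (i.e. daily mood reports) will raise awareness of personal severity of depression". Under Eligibility Criteria, a score of 1 or more on PHQ-9 item 9 is one of the routes to a positive screen.

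The baseline call collects "the CSSRS scale & suicide scales, quality of life ratings, treatment history, barriers to treatment, readiness for treatment". At weeks 4 and 12 the assessor will "collect measures on depression, anxiety, mania, and suicide symptoms, the CSSRS, quality of life ratings, barriers to treatment, readiness for treatment". The same list includes "treatment utilization and history since last assessment".

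Three kinds of comparison are stated:

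- Readiness, by a generalized linear mixed model nesting for site (Study Objectives, Hypothesis 1b, and Statistical Considerations).
- Use of behavioral and physical health services, T2C against TAU, as an exploratory aim (Study Objectives, Aim 2).
- The RE-AIM components, where the outcome entry reads "E)fficacy: The impact of T2C on MH treatment initiation and engagement".

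Clinical variables are also tested between groups, but only at baseline and in order to choose covariates. On records, the baseline section says "Electronic medical record information will be used to supplement treatment and service utilization and uptake of the T2C intervention".

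**The concern.** The population includes youths with suicidal thoughts, and the intervention deliberately draws attention to depression and suicidality. The plan assumes this is low risk and collects the data that could check the assumption. It then gives those data no role after baseline. No harm hypothesis, safety table or event count by condition is described.

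Two consequences follow. A report that kept to the plan could present a gain in readiness as the result while leaving suicidal ideation and behaviour unexamined by condition. And Aim 2 is worded so that a first appointment after referral and a suicide-related emergency visit are both service use. A higher rate under T2C would then mix an intended effect with a possible adverse one.

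**Working it through.** **Collection set against analysis**

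| Measure | Collected at | Stated T2C v TAU analysis after baseline |
|---|---|---|
| Readiness | Baseline, weeks 4 and 12 | Yes, mixed model |
| Service use | Baseline history, weeks 4 and 12, records | Yes, Aim 2 (exploratory) |
| Treatment initiation and engagement | From treatment-use data | Yes, RE-AIM Efficacy |
| CSSRS | Baseline, weeks 4 and 12 | None stated |
| Suicide scales (baseline), suicide symptoms (follow-up) | Baseline, weeks 4 and 12 | None stated |

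Statistical Considerations says that baseline and follow-up measures are mapped onto RE-AIM. Each component is defined there, by participation, treatment initiation and engagement, PCP referral, completion or continued use. None is defined by symptoms or suicidality, so that sentence does not supply the comparison.

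**Timing**

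The texts last about one week (days 0 to 7) and the first follow-up call is at week 4 (day 28). A question asked at day 28 reaches back to the end of the text week only if its reference period exceeds 28 − 7 = 21 days, and covers the whole week only if it reaches 28 days. The documents give no reference period for the suicide measures. Whether the text week is covered is therefore unknown.

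**What an added comparison could show**

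The plan states no power, effect size, SD or event rate, so there is no figure of its own to reproduce. From the documents: 50 adolescents, 2 clinics. Assumed: splits of 25/25, 20/30 or 15/35, two-sided 5% level, no dropout, no clustering or period effect.

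1. Half-width of the 95% interval for a difference in means, in SD units: 1.96 × √(1/n₁ + 1/n₂).
   - 25/25: 1.96 × √0.080 = 0.55
   - 20/30: 1.96 × √0.0833 = 0.57
   - 15/35: 1.96 × √0.0952 = 0.61
2. Power for a 0.5 SD worsening: Φ(0.5/√(1/n₁ + 1/n₂) − 1.96). For 25/25 this is Φ(1.768 − 1.96) = 42%. The other splits give 41% and 37%.
3. Power for a binary event at 25/25, normal approximation with pooled variance under the null, at assumed rates: 10% for 5% v 10%; 16% for 10% v 20%; 42% for 10% v 30%.
4. Exact two-sided 95% upper bound for zero events in n youths: 1 − 0.025^(1/n).
   - n = 25: 13.7%
   - n = 35: 10.0%
   - n = 15: 21.8%

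The bound in step 4 is a rate within the T2C group alone. It shows how little an absence of events would exclude and does not estimate the difference from TAU. Allowing for site and period with two clinics would make steps 1 to 3 less precise.

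**The case against.** The strongest reply is that this is a 50-youth, two-clinic feasibility study. The low-risk statement is a reason for the design, offered alongside stakeholder demand, and the protocol plans no conclusion that T2C is safe. The arithmetic above also shows that an added comparison would be imprecise. All of that stands, and it is why the remedy is descriptive. It does not explain why suicide data gathered at weeks 4 and 12 should have no stated use by condition.

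Several stronger readings are tempting, but the documents do not support them:

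- **That the protocol contradicts itself.** Raising perceived severity so as to motivate care is not raising actual severity. The low-risk statement is untested, not refuted.
- **That suicide data are certainly collected alike under TAU.** The consent, baseline and follow-up sections describe the calls together with T2C onboarding, and no TAU schedule is given. Collection under TAU is an inference, though a reasonable one, because readiness comes from the same calls and is to be compared with TAU.
- **That suicidality is never compared.** Baseline clinical variables are tested between groups and may include it. The gap is after baseline.
- **That the follow-up questions miss the text week.** No reference period is stated, so a short one cannot be assumed.
- **That Aim 2 cannot be interpreted, or that records miss crisis events.** Crisis visits may well be captured as service use. The point is only that nothing says they will be reported separately.

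**Conclusion.** The point holds as a gap in the analysis plan. Suicide symptoms and the CSSRS at weeks 4 and 12 have no stated post-baseline comparison by condition, in a trial that can enrol youths on a suicidality item and whose rollout rests partly on an unsupported expectation of low harm. The documents give no evidence that T2C is harmful, and none is implied here.

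No event rate is given, so the size of any missed effect cannot be stated. What can be stated is the limit of the remedy. Under the assumed splits, a difference in scores would carry a 95% interval of about ±0.55 to 0.61 SD, and zero events in 15 to 35 T2C youths would leave an upper bound of 21.8% to 10.0% (13.7% for 25). A null result could not establish absence of harm. The change is still worth making, because it decides whether the trial reports anything about harm by condition. The readiness analysis is not affected.

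**What to change.** 1. **Statistical Considerations.** Add a descriptive T2C v TAU comparison of suicidal ideation and behaviour (CSSRS and suicide symptoms) at weeks 4 and 12: counts with exact 95% intervals, and change from baseline where the same instrument is used at both times. State that the comparison is descriptive and cannot establish absence of harm.
2. **Follow Up assessment phone calls.** Confirm that TAU youths are assessed on the same week 4 and week 12 schedule. Measure suicidal behaviour since the last assessment in both conditions, so that the text week is covered. Treatment use already has this reference period.
3. **Aim 2 and the record extraction.** Report suicide-related emergency visits and admissions separately from linkage visits, in both conditions.

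The cost is analysis wording, one table, a stated reference period and one more field in a planned record extraction. No visits are added if TAU youths are already on the same schedule. If they are not, the readiness comparison lacks its TAU data too, and that must be settled in any case. The downside is wide intervals and a less favourable safety statement than the present assumption.
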